Prior studies of use of CGM in the inpatient non-ICU setting have indicated that CGM is effective in evaluating glycemic trend and allowing for interventions to prevent hypoglycemia based on studies utilizing professional CGM technologies compared to fingerstick blood glucose values.³ Furthermore, a recently conducted study of 8 critically ill subjects with diabetes that wore Freestyle Libre CGM's during their ICU stay demonstrated high test-retest reliability and acceptable accuracy when compared with arterial blood glucose measurements.⁴ However, there is currently very limited data regarding the use of CGM technology in the perioperative setting. Current standards of care by the American Diabetes Association advise monitoring blood glucose while subjects are taking nothing by mouth and that rapid or short acting insulin be administered to target perioperative blood glucose of 80-180 mg/dL.⁵ Standard of care protocol during surgery includes blood glucose checks at 60 minute intervals and when clinically indicated. A dose of correction insulin is recommended to be administered if blood sugar is greater than 180 mg/dL.

A recent small study evaluated use of Dexcom G6 CGM technology in the OR and Cardiac ICU in 13 subjects without diabetes mellitus undergoing coronary artery bypass surgery.⁶ In some subjects

Protocol version: 02/07/2024

intermittent signal loss was noted during operative time with some sensors continuing to function in the postoperative setting. We recently studied CGM technology in the OR in 76 subjects at Wake Forest University School of Medicine undergoing noncardiac surgery.⁷ We compared current standard of care blood glucose fingersticks to CGM data utilizing both the Dexcom G6 CGM and the Freestyle Libre 2.0 CGM.

Additional studies are needed to further evaluate the possible benefits and potential limitations of CGM technology in the perioperative setting. We are interested in how CGM technology could improve glycemic management in the preoperative setting. We aim to evaluate utilization of CGM technology in the preoperative setting by enrolling a total of 220 subjects with diabetes mellitus. The original feasibility study included 20 subjects who all were wearing the Freestyle Libre Pro CGM device in an effort to determine the feasibility of wearing the device for up to 14 days prior to their scheduled surgery. No randomization was involved in that initial cohort. This expanded study will now randomize subjects to utilization of the Freestyle Libre Pro device versus Freestyle Libre 2 device. Subjects will be enrolled during the preoperative appointment and have a 50% chance of having a Freestyle Libre Pro CGM device vs Freestyle Libre 2 device placed during the preoperative appointment. Current standard of care with monitoring glycemic range utilizing point of care blood glucose fingersticks, serum glucose, as well as arterial glucose as indicated will be utilized for all subjects. Additionally, patients randomized to the Freestyle Libre 2 device will be instructed to scan the sensor every 8 hours at home.

Objectives

1-Investigate time in range during preoperative period prior to the day of surgery in patients wearing CGM;

2-Compare average glucose from holding room in patients wearing Freestyle Libre Pro CGM vs. patients wearing Freestyle Libre 2 CGM

- To evaluate use of CGM technology in the preoperative setting: evaluate feasibility of placement of CGM during preoperative clinic visit
- To assess how CGM technology could improve glycemic management in the perioperative setting

Methods and Measures

Design

- This is a prospective analysis of a cohort study of subjects with diabetes mellitus undergoing surgery.
- Prospectively, subjects will be undergoing surgery that does not involve the upper extremity given the potential need for CGM placement site.
- We will be analyzing data obtained from the Freestyle Libre Pro and Freestyle Libre 2, which will be placed on a randomized group (1:1) of consented subjects. 100 subjects will receive the Freestyle Libre Pro CGM and 100 subjects will receive the Freestyle Libre 2 CGM.
- Subjects will wear CGM throughout perioperative period.
- CGM will be in use for up to 14 days (total preoperative + postoperative, or until discharge, whichever comes first).
- For the Freestyle Libre 2 CGM group, an endocrinologist will review the CGM data within a week of placement of CGM, and may recommend medication changes based on CGM data to the study subject.
- Regardless of the group, all subjects will receive standard of care during surgery and hospitalization with fingerstick blood glucose checks at Atrium Health Wake Forest Baptist. It is standard of care for fingerstick blood glucose checks to occur upon arrival to preoperative holding bay and upon arrival to Post Anesthesia Care Unit. Intraoperative

and postoperative glucose checks are at the discretion of the anesthesiologist while in the recovery area, and at the discretion of the surgical team when on the postoperative floor.

- CGM device will be removed by research team prior to discharge.

Setting

The study takes place at an academic medical center, Atrium Health Wake Forest Baptist in Winston- Salem, NC.

Subjects Selection Criteria

- **Inclusion Criteria**

- 18 years of age or older
- Diagnosed with diabetes mellitus
- Undergoing inpatient surgery at Atrium Health Wake Forest Baptist
- Smartphone compatible with the Freestyle Libre 2 CGM phone application

- **Exclusion Criteria**

- Undergoing surgery that would limit the placement of CGM to the posterior aspect of the upper extremity
- CGM devices do not pose a risk to mother or fetus, so pregnancy will not be an exclusion criteria.
- Undergoing cardiac surgery

- **Sample Size**

There will be a total of 220 subjects selected during preoperative evaluation appointment at Atrium Health Wake Forest Baptist. In order to get 220 evaluable subjects, a total of up to 240 subjects may be consented. This total of subjects includes the 20 pilot subjects that were previously enrolled under this protocol.

Interventions and Interactions

- Subjects will be identified at time of preoperative appointment at Atrium Health Wake Forest Baptist. Similar to our previous CGM study, the research team will review subjects scheduled for Preoperative Assessment Clinic visit for inclusion criteria and exclusion criteria. Subjects that meet criteria will be approached by research team during Preoperative Assessment Clinic visit in a private clinic room. This is a private clinic room with adequate space to discuss study participation.
- Written informed consent will be obtained from individuals that meet above inclusion criteria by a member of the research team.
- Once consent has been obtained, the subjects will be randomized to receive either the Freestyle Libre Pro or Freestyle Libre 2. CGM will be placed on the subject prior to their discharge from their preoperative assessment clinic visit with contact information for research staff being given for any issues that may arise.
- Research staff will then meet the subject in the holding room on the morning of surgery to ensure device remains in place. The subject will then be followed during the perioperative period.
- Chart review will occur to collect data on the standard of care glucose values obtained from preoperative holding bay and post anesthesia care unit.
- The CGM device will be removed prior to discharge.
- Typical standard of care blood sugar collection occurs in preoperative holding bay (before subject is taken back to the OR) and upon arrival to the post anesthesia care unit (after surgery). Intraoperative blood sugar collection is at the discretion of the anesthesiologist.

- For all consented study subjects, we will retrospectively review the CGM data to compare to 1. The time of the preoperative blood sugar collection and 2. The time of the post anesthesia care unit blood sugar collection. We will retrospectively note insulin administration in this study.
- Data collection for each subject will include subject demographics, status of diabetes mellitus diagnosis, comorbid conditions, all blood glucose values during admission, all chemistry laboratory during admission, as well as data obtained from the Freestyle Libre Pro and Freestyle Libre 2 CGM that is worn throughout the perioperative and postoperative setting.

Outcome Measure(s)

- Proportion of subjects who present on day of surgery with CGM still in place and functioning
- Comparison utilizing Freestyle Libre 2 CGM in the perioperative setting for subjects with diabetes mellitus compared with Freestyle Libre Pro CGM with current standard of care utilizing point of care blood glucose fingerstick.
- Subject satisfaction with CGM
- Comparison of number of events of hyperglycemia (>180 mg/dL) on day of surgery (preoperative holding room and post anesthesia care unit) in subjects wearing Freestyle Libre Pro CGM vs. subjects wearing Freestyle Libre 2 CGM

Analytical Plan

Results will be analyzed comparing glycemic data from point of care fingerstick blood glucose values as well as serum glucose values of patients wearing Freestyle Libre Pro CGM to patients wearing Freestyle Libre 2 CGM and will be assessed statistically. Other inferential statistical analysis will be conducted as appropriate.

Human Subjects Protection

Subject Recruitment Methods

Only those subjects who have diabetes mellitus and are undergoing inpatient surgery at Atrium Health Wake Forest Baptist will be recruited for this study. Subjects will be identified with the assistance of the Anesthesiology team on day of preoperative assessment prior to planned surgery.

Informed Consent

Signed informed consent will be obtained from each subject by the investigators listed above at time of admission to Atrium Health Wake Forest Baptist. Risks, benefits, and alternatives will be explained to each subject.

Confidentiality and Privacy

Confidentiality will be protected by collecting only information needed to assess study outcomes, minimizing to the fullest extent possible the collection of any information that could directly identify subjects, and maintaining all study information in a secure manner. To help ensure subject privacy and confidentiality, only a unique study identifier will appear on the data collection form. Any collected subject identifying information corresponding to the unique study identifier will be maintained on a linkage file, stored separately from the data. The linkage file will be kept secure, with access limited to designated study personnel. Following data collection, subject identifying information will be destroyed (3 years after closure of the study by file deletion), consistent with data validation and study design, producing an anonymous analytical data set. Data access will be limited to study staff. Data and records will be kept locked and secured, with any computer data password protected. No reference to any individual subject will appear in reports, presentations, or publications that may arise from the study.

Data and Safety Monitoring

The principal investigator will be responsible for the overall monitoring of the data and safety of study subjects. The principal investigator will be assisted by other members of the study staff.

Reporting of Unanticipated Problems, Adverse Events or Deviations

Any unanticipated problems, serious and unexpected adverse events, deviations or protocol changes will be promptly reported by the principal investigator or designated member of the research team to the IRB and sponsor or appropriate government agency if appropriate.

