APPENDIX:

Timeline

1. Day 1: Preoperative Assessment Clinic visit.
 - a. The timing of this visit varies, but is often a few days to a week or so prior to day of surgery.
 - b. Potential subject will be identified by research team (like we did for our previous CGM study)
 - c. Consent by PI or clinical research staff
 - d. Device placement (CGM) by research team
 - e. Subject wearing Freestyle Libre 2 CGM will be given protocol to scan the sensor at least every 8 hours at home. Otherwise, subjects should follow their usual routine for their blood sugar management.
2. Day 2 – 13: Day of surgery
 - a. The timing of this varies, but is often a few days after PAC visit.
 - b. If the patient is wearing a Freestyle Libre 2 CGM, an endocrinologist will review the data remotely within a week of placement and may recommend medication changes prior to day of surgery.
 - c. Blood sugar obtained in preoperative holding room bay by preoperative nurse (this is our standard of care at Atrium Health Wake Forest Baptist, this will not need to be protocolized, preoperative nurse should follow their usual routine for a subject with diabetes).
 - d. Device checked by research team in preoperative holding room (that CGM is still in place and functional).
 - e. If subject is discharged to home, CGM will be removed in PACU by research team prior to discharge.
3. Up to day 14: Post operative day 1
 - a. If subject stays overnight, CGM will be removed in subject hospital room by research team prior to discharge.

References

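### The randomised comparison is worded as device against device, but the Libre 2 arm is a package with home scanning and endocrinologist review, and delivery of that review is not among the listed data

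*Combined protocol and SAP*

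**What the plan says.** All references are to the combined protocol and SAP.

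**The contrast as stated.** The paragraph before Objectives says: "This expanded study will now randomize subjects to utilization of the Freestyle Libre Pro device versus Freestyle Libre 2 device". Objective 2 is: "Compare average glucose from holding room in patients wearing Freestyle Libre Pro CGM vs. patients wearing Freestyle Libre 2 CGM". The second and fourth items under Outcome Measure(s) and the Analytical Plan also compare Libre Pro with Libre 2 wearers. None of these statements mentions endocrinologist review. A further aim under Objectives is: "To assess how CGM technology could improve glycemic management in the perioperative setting".

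**What the arms receive.** Under Design: "For the Freestyle Libre 2 CGM group, an endocrinologist will review the CGM data within a week of placement of CGM"; the endocrinologist "may recommend medication changes based on CGM data to the study subject". The paragraph before Objectives adds that "patients randomized to the Freestyle Libre 2 device will be instructed to scan the sensor every 8 hours at home". The Appendix timeline repeats both for Libre 2 only. No section gives the Libre Pro arm a review before surgery. Interventions and Interactions provides only for retrospective review of CGM data, in all subjects.

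**Timing.** The Appendix puts placement on Day 1 and then gives "Day 2 – 13: Day of surgery". It also says that the recommendations may be made ahead of the day of surgery.

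**Data.** Interventions and Interactions states: "Data collection for each subject will include subject demographics, status of diabetes mellitus diagnosis, comorbid conditions, all blood glucose values during admission". The list goes on to laboratory chemistry and sensor data. Insulin given is noted retrospectively. Nothing is listed on whether or when the review took place, what was advised, or whether the advice was followed.

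**The concern.** A recommendation to change medication acts directly on the endpoint, glucose on the day of surgery. If Libre 2 subjects arrive with lower glucose, the wording of Objective 2 and the Analytical Plan invites credit to the sensor, and the CGM-technology aim invites credit to CGM in general. The specialist review could have produced the difference.

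The reverse case matters as much. If the arms look alike, the package may not work, or the review may often have come too late or not at all. Without a record of delivery, a reader cannot tell which.

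**Working it through.** **Figures in the plan.** The only relevant figures are counts: 100 + 100 randomised + 20 pilot = 220, which agrees with the stated total. The pilot subjects were not randomised and stand outside this contrast. The documents give no effect size, SD, significance level, power or delivery rate, so there is no effect calculation to reproduce.

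**Step 1: components by arm.**

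| Component | Libre Pro | Libre 2 |
|---|---|---|
| Wears a CGM | yes | yes |
| Device | Pro | 2 |
| Instruction to scan every 8 hours at home | no | yes |
| Endocrinologist review, possible medication changes | no | yes |

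Three rows differ and there is one randomised contrast. The first row does not differ, so no contrast bears on CGM against no CGM.

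**Step 2: timing.** Counting a week as seven days, a review due within a week of Day 1 may come as late as Day 1 + 7 = Day 8. Surgery may fall on Days 2 to 13, and the Appendix says that it is often a few days after the clinic visit. Surgery on Days 2 to 7 would therefore precede the end of the review window. This shows that review after surgery is possible. It does not show how often, because the documents give no distribution of surgery dates or of actual review times.

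**Step 3: what the trial estimates.** As a simple additive description, let T = D + π·m, where

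- T is the arm difference in mean holding-room glucose (Libre 2 minus Libre Pro);
- D is the effect of device plus scanning;
- π is the share of the Libre 2 arm reviewed before surgery;
- m is the mean effect of a delivered review.

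The data estimate T. Nothing listed gives π, and no comparison gives D or m.

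**Step 4: illustration. Every input here except the arm size is assumed.** Take T = −20 mg/dL and D = T − π·m:

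| π | m = 0 | m = −10 | m = −20 | m = −30 |
|---|---|---|---|---|
| 0.3 | −20 | −17 | −14 | −11 |
| 0.6 | −20 | −14 | −8 | −2 |
| 0.9 | −20 | −11 | −2 | +7 |

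One observed difference is compatible with D from −20 to +7 mg/dL.

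For the null case, take D = 0, m = −20, SD = 50 mg/dL, 100 per arm and two-sided 0.05. The standard error is 50 × √(2/100) = 7.07, and power ≈ Φ(20π/7.07 − 1.96):

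| π | Mean difference (absolute) | Power |
|---|---|---|
| 1 | 20 | 81% |
| 0.75 | 15 | 56% |
| 0.5 | 10 | 29% |
| 0.25 | 5 | 11% |

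Under these assumptions the unlisted quantity π largely decides whether an effective review shows up at all.

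**The case against.** The strongest reply is that nothing is hidden. Scanning and review are set out openly as procedures of the Libre 2 arm, the device names can be read as arm labels, and a randomised comparison of packages is a legitimate design. This stands: the estimate of the package effect is valid. A reader might infer that the trial identifies nothing useful, and the documents do not support that.

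Other parts of the reply also stand.

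- The CGM-technology aim is exploratory. No section claims an isolated device effect or an effect against no CGM, so misattribution is a risk created by the wording and not a stated conclusion.
- Only two of the four outcomes compare the devices. Sensor retention and satisfaction are not worded as comparisons. Objective 1 and the feasibility aim do not depend on attribution to the device either.
- The Appendix shows that recommendations are intended before surgery.
- The data list says what will be included and need not be exhaustive, so the fair statement is that delivery is not listed, not that it will go unrecorded.
- Scanning may be part of using the Libre 2; the documents do not say whether it is separable.

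The opening of the background was not available for this check, so a rationale for the package may appear there. It would not alter the wording of the objectives, outcomes and analysis.

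The reply leaves two gaps: those statements do not name the package, and no listed item shows whether its most active component reached the subject in time.

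**Conclusion.** The point holds as a matter of labelling and of recording delivery. The trial can answer whether Libre 2 with scanning and endocrinologist review gives different day-of-surgery glucose from Libre Pro without them. It cannot say how much of a difference is due to the device, or what CGM itself contributes. A null result could not be told apart from non-delivery of the review.

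The size of either effect cannot be derived from the documents; the mg/dL and power values above illustrate the mechanism under assumed inputs. A reader might put the device's share at somewhere between 0% and 100% of the difference. Nothing in the documents supports those bounds, and the illustration passes them: +7 against −20 is a share of −35%. A reader might also infer that many Libre 2 subjects will go unreviewed. The timeline shows only that some may.

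The conclusion rests on two readings: that the Libre Pro arm gets no comparable review before surgery, since none is described, and that the data list is meant as the working list. It is a worthwhile, inexpensive improvement and not a fatal flaw.

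**What to change.** 1. Reword Objective 2, the second and fourth outcomes and the Analytical Plan as *Libre 2 with subject scanning plus endocrinologist review* against *Libre Pro without these, with usual care*, analysed as randomised. The Analytical Plan does not currently state an as-randomised analysis.
2. Limit the conclusion, including the one drawn for the CGM-technology aim, to that strategy.
3. Add four Libre 2 fields: date of review; review before surgery (yes/no); change recommended (yes/no); change followed (yes/no). The first three can be logged at or from the review. The last must be asked, and staff already meet the subject in the holding room on the morning of surgery.
4. Report these fields descriptively beside the as-randomised result. State that they describe delivery and do not isolate the device effect, because the review is given in one arm only and uptake arises after randomisation.

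The cost is a narrower claim about the device, a few extra fields and one extra question. Arms, sample size and clinical care are unchanged. The fields should be in place prospectively, since uptake is hard to reconstruct later.

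### No pre-randomisation measure of glycemic control is listed for either arm, so the holding-room comparison can be neither described nor adjusted by prior control

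*Combined protocol and SAP*

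**What the plan says.** Objective 2 of the protocol is to "Compare average glucose from holding room in patients wearing Freestyle Libre Pro CGM vs. patients wearing Freestyle Libre 2 CGM". The Outcome Measure(s) section adds a between-arm count of hyperglycemic events above 180 mg/dL in the holding room and the post anesthesia care unit.

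The data to be collected are listed at the end of Interventions and Interactions: demographics, diabetes diagnosis status, comorbid conditions, then "all blood glucose values during admission, all chemistry laboratory during admission". The sensor readings from both devices complete the list. HbA1c is not named, nor is any glucose value from the clinic visit or earlier.

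The same section gives the order of events: "Once consent has been obtained, the subjects will be randomized to receive either the Freestyle Libre Pro or Freestyle Libre 2". After that, "CGM will be placed on the subject prior to their discharge from their preoperative assessment clinic visit". The Timeline's Day 1 covers identification, consent, device placement and the Libre 2 scanning instruction (at least every 8 hours), with no glycemic measurement or chart extraction.

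In the Libre 2 arm only, according to Design, "an endocrinologist will review the CGM data within a week of placement of CGM, and may recommend medication changes". The Analytical Plan names no covariate and no adjustment.

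**The concern.** Any adult with diabetes having inpatient non-cardiac surgery can qualify, with no limit on glycemic control, so prior control may differ widely between subjects. It is a natural candidate to predict glucose on the morning of surgery, although the documents give no figure for that relation.

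If prior control is not recorded, three things are lost. The report cannot show whether the arms were alike on it. The analysis cannot use it to reduce residual variance. And if some randomised subjects are not evaluable, nobody can check whether those who remain are still comparable. The Sample Size section allows up to 240 consented for 220 evaluable and does not define evaluable.

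**Working it through.** **1. Is any listed glycemic value pre-randomisation?**

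| Source | When it starts | Before randomisation? |
|---|---|---|
| Chart glucose and chemistry | Admission | No |
| CGM, both arms | Clinic visit, after allocation | No |
| Diabetes diagnosis status | Not defined | Possibly, but not stated to be a measure of control |
| Timeline Day 1 | Clinic visit | No glycemic value listed |

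CGM does start before admission; Objective 1 depends on that ("Investigate time in range during preoperative period prior to the day of surgery in patients wearing CGM"). But it follows allocation, and only Libre 2 subjects are told to scan at home and have their data reviewed. Adjusting for early CGM readings would risk adjusting for part of the effect under study.

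**2. The plan's own figures.** The totals agree: 20 pilot + 100 + 100 = 220, and 1 − 220/240 = 8.3% allowed loss. No alpha, power, effect size or SD is given, so there is no power calculation to reproduce.

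**3. Detectable difference.** From Design: n = 100 per arm. Assumed: two-sided alpha 0.05, 80% power, and a correlation r of 0.3 to 0.5 between the baseline value and holding-room glucose.

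- Unadjusted: (1.960 + 0.842) × sqrt(2/100) = 2.802 × 0.1414 = 0.396 SD.
- Adjusted: 0.396 × sqrt(1 − r²).
- Sample size per arm that an unadjusted analysis would need to match: 100/(1 − r²).

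| r | sqrt(1 − r²) | Detectable difference | Power at 0.396 SD | Matching n per arm | mg/dL at assumed SD 40 / 50 / 60 |
|---|---|---|---|---|---|
| none | 1.000 | 0.396 SD | 80% | 100 | 15.8 / 19.8 / 23.8 |
| 0.3 | 0.954 | 0.378 SD | 83.6% | about 110 | 15.1 / 18.9 / 22.7 |
| 0.5 | 0.866 | 0.343 SD | 89.9% | about 133 | 13.7 / 17.2 / 20.6 |

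These figures suppose that every subject has a baseline value. If only a fraction p has one, the variance reduction falls from r² to roughly p × r², so the gain is smaller. They apply to mean glucose and do not carry over directly to the count of events above 180 mg/dL.

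**4. Chance imbalance.** The difference between arms in a standardised baseline has SE sqrt(2/100) = 0.141 SD and a 95% range of ±1.96 × 0.141 = ±0.277 SD. At that limit it carries 0.277 × 0.3 = 0.083 SD to 0.277 × 0.5 = 0.139 SD into the outcome, or 4.2 to 6.9 mg/dL at an assumed SD of 50.

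This is not an extra error. The unadjusted 95% half-width at that SD is 1.96 × 0.1414 × 50 = 13.9 mg/dL and already contains it. Adjustment would narrow the half-width to 13.9 × 0.954 = 13.2 or 13.9 × 0.866 = 12.0 mg/dL.

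**The case against.** The strongest reply is that allocation is randomised 1:1, so the unadjusted comparison is valid without any baseline. That stands. A reader might infer from the missing baseline that the holding-room comparison is biased, or that 4 to 7 mg/dL must be added to its uncertainty. The documents do not support either: randomisation makes the comparison unbiased in expectation, and its confidence interval already includes chance imbalance. The protection covers subjects as randomised, however. It does not extend automatically to an evaluable subset, or to the 20 non-randomised pilot subjects.

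Two other strong readings also fail. A reader might take it that all glucose collection begins at admission; the CGM data in the same sentence begin days earlier. A reader might also suppose that by admission the Libre 2 intervention has always taken effect. The Timeline says "an endocrinologist will review the data remotely within a week of placement and may recommend medication changes prior to day of surgery", but it also allows surgery from Day 2, so some subjects may reach the holding room with no review or change.

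It can further be said that the data list is not declared exhaustive, that diabetes diagnosis status is undefined, and that admission is used loosely, since the Informed Consent section places consent at admission while Interventions and Interactions places it at the clinic visit. These points show ambiguity, not a planned baseline. The Confidentiality and Privacy section restricts collection to what the outcomes require, so an item nobody listed may well not be collected.

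Lastly, the Analytical Plan names no test or model at all, so the covariate is one part of a wider gap. That is true, but a missing model can still be written later, whereas a baseline that nobody extracted may no longer be recoverable once identifiers are destroyed.

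**Conclusion.** The point holds as a matter of precision and of checking comparability, not of bias. No pre-randomisation measure of glycemic control is listed for either arm, and none is planned as a covariate.

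The gain forgone is modest but real: a detectable difference of 0.396 SD that could be about 0.378 SD (r = 0.3) or 0.343 SD (r = 0.5), equivalent to roughly 10 to 33 more subjects per arm. This rests on 100 analysed per arm, two-sided 0.05 and 80% power, with r assumed and baseline values complete. Because the remedy is cheap, it should be made.

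**What to change.** - In Interventions and Interactions, widen the collection window for glucose and laboratory values to before randomisation and during admission.
- At Timeline Day 1, extract from the chart for each subject the most recent HbA1c dated on or before the clinic visit, within a look-back period fixed in advance, and the current home diabetes treatment.
- Present both by arm, for all randomised subjects and for those evaluable.
- In the Analytical Plan, prespecify HbA1c as the covariate in the between-arm holding-room glucose comparison, and keep subjects without a value by means of a missing indicator.
- If a prior laboratory glucose is also extracted, report it as a separate variable. It is on a different scale and should not stand in for HbA1c in the same covariate.

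The cost is a few extra fields in a chart review that the study already does, with no new blood draw. Some subjects will lack a recent HbA1c. The documents do not say how many, and the gain shrinks as that number grows.

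### Must the plan change because it names no primary outcome and leaves preoperative time in range undefined?

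*Combined protocol and SAP*

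**What the plan says.** **Objectives.** Two numbered objectives head the list: "1-Investigate time in range during preoperative period prior to the day of surgery in patients wearing CGM" and "2-Compare average glucose from holding room in patients wearing Freestyle Libre Pro CGM vs. patients wearing Freestyle Libre 2 CGM". Two bulleted aims on feasibility and glycemic management follow. None is ranked as primary.

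**Design.** Allocation is 1:1, with 100 subjects per device. The section adds "We will be analyzing data obtained from the Freestyle Libre Pro and Freestyle Libre 2" but gives no method.

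**Interventions and Interactions.** For every subject, "we will retrospectively review the CGM data to compare to 1. The time of the preoperative blood sugar collection", with the recovery-unit collection as the second time point. Data collection includes "all blood glucose values during admission" and the sensor data.

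**Outcome Measure(s).** There are four: "Proportion of subjects who present on day of surgery with CGM still in place and functioning"; a general Libre 2 versus Libre Pro comparison in the perioperative setting, alongside standard fingersticks; satisfaction; and day-of-surgery hyperglycemia events above 180 mg/dL. Time in range is not among them.

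**Analytical Plan.** The first sentence reads "Results will be analyzed comparing glycemic data from point of care fingerstick blood glucose values as well as serum glucose values", compared by device. The only other statement is "Other inferential statistical analysis will be conducted as appropriate".

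**The concern.** Time in range is the first-listed objective, yet nothing downstream picks it up. Its window closes before the day of surgery, whereas the one CGM comparison that is described uses two day-of-surgery times.

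The window also varies a great deal in length, because the sensor goes on at Day 1 and surgery falls anywhere from Day 2 to Day 13 (Appendix, Timeline). Two analysts could weight readings or subjects differently, keep or drop short recordings, or choose different limits, and so report different figures.

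The arms are not handled alike before surgery. Only Libre 2 subjects are told to scan at home, and only they have endocrinologist review with possible medication changes. A pooled figure and a by-arm figure therefore answer different questions, and completeness could differ by arm. With no primary named, the headline could be chosen after results are seen.

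**Working it through.** The plan gives no figure for time in range to reproduce. The check sets the sections side by side and sizes each open choice.

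1. **Is time in range named?** It is named in 0 of 4 outcome measures and not in the Analytical Plan. Two glucose comparisons are written out: fingerstick and serum by device, and CGM at the two blood-collection times. Neither reaches Objective 1's window. The second outcome measure is a further written comparison. It is set in the perioperative period, and Design has the sensor worn throughout that period, so it is vague but not shown to exclude the preoperative days.

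2. **Is Objective 2's glucose source open?** Only partly. Design makes a fingerstick on arrival in the holding bay standard care. The Timeline has the preoperative nurse obtain that value, Interventions collects it by chart review, and the Analytical Plan compares fingerstick and serum values. What remains open is which of those two to use when both exist.

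3. **Window and weights.** Full days before surgery run from 0 (Day 2 surgery) to 11 (Day 13 surgery, Days 2 to 12). Let p be the recorded fraction of Day 1. If readings are pooled, the Day 13 to Day 2 weight ratio is (11 + p)/p:
   - p = 1: 12/1 = 12.0
   - p = 0.5: 11.5/0.5 = 23.0

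   The Timeline says the clinic visit is often a few days to a week or so before surgery. Taking Day 8 against Day 4 as a more typical pair, the ratio is (6 + p)/(2 + p):
   - p = 1: 7/3 = 2.3
   - p = 0.25: 6.25/2.25 = 2.8

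   If each subject's percentage is computed first, the ratio is 1 in every case.

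4. **Limits.** The only glucose range in the document is the 80-180 mg/dL care target in the Background. The hyperglycemia outcome uses the same upper value. Moving the lower limit from 80 to 70 adds 0.3 to 3.8 percentage points, assuming lognormal glucose with mean 150-180 mg/dL and CV 30-40%. A different upper limit would matter far more. With normally distributed glucose, mean 150-190 mg/dL and CV 25-35% (also assumed), limits of 80-180 give 39% to 76% in range and 70-140 give 14% to 38%. Nothing in the document points to an upper limit other than 180.

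5. **Minimum sensor data.** Scanning every 8 hours is 24/8 = 3 scans a day. If an unscanned block is lost (the document does not say), one miss a day leaves 2/3 = 66.7% of readings. A 60% minimum then keeps the subject and a 70% minimum drops them. But any exclusion on completeness could select differently by arm after randomisation, so imposing a minimum is not clearly better than using all available data.

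6. **Pilot subjects.** 20 + 100 + 100 = 220, which agrees with Sample Size. Counting the 20 pilot subjects as Libre Pro wearers would make them 20/120 = 16.7% of that group. Design, however, ties the analysis to a randomised group of 100 and 100, and the Background says the pilot was not randomised.

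7. **Multiplicity.** Three independent arm comparisons at an assumed 0.05 give 1 - 0.95³ = 14.3%. If the second outcome is not an arm contrast, two give 1 - 0.95² = 9.8%. The plan states no test level and makes no confirmatory claim, so these figures describe an assumed testing scheme.

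**The case for a change.** The best case for a change is that this is the leading objective of a randomised study, that even a descriptive estimate needs a definition, and that supplying one costs a few sentences because the data are already being collected. Written before analysis, it would protect against selective choice; written afterwards, it would not. The 80-180 range is a care target and not an endpoint definition, and the general sentence on other inferential analysis settles nothing.

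The factual part stands: no primary, no limits and no method are stated. The point about timing stands too, and so does the point that pooled and by-arm time in range are different quantities, since the arms receive different preoperative care.

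What does not follow is that the plan will produce a wrong result. The harmful options (pooling readings across subjects, mixing the pilot into a randomised arm, ignoring the arms) are ones the document does not propose, and the pilot reading runs against its Design section. The remedy amounts to asking the sponsor to record choices that are its own to make, and the one specific rule that could be offered, a minimum amount of sensor data, rests on an undocumented data-loss assumption and could itself introduce selection by arm.

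**Conclusion.** The gap is real, but it is one that analysts fill sensibly, so no change follows. The ordinary reading is a percentage per subject, from placement to the end of the day before surgery, using all available readings, summarised by randomised arm with the amount of sensor data shown. That removes the 12-to-1 or larger weighting problem. The randomised glucose comparison is unaffected.

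Two choices remain with the sponsor: the limits, where the document offers only 80-180 mg/dL, and fingerstick or serum for Objective 2 when both exist. With no primary named, no single result should be presented as confirmatory.

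This conclusion assumes per-subject, by-arm analysis, with the pilot kept apart from the randomised groups. It also rests on the text available: the opening part of the document could not be read, although the objectives, outcome and analysis sections could.
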